**Table 2 Study groups, intervention and blinding**

Study groups	Number of participants	Age (Min-Max)	Study interventions	Timing of intervention		
				Visit 1	Visit 4	Visit 8
HBs-alum	23-30	18-45 years	Engerix-B	X	X	X
HBs-AS03	23-30		HBsAg/AS03 A	X	X	
HBs-AS04	23-30		Fendrix	X	X	
HBs-AS37_50	23-30		HBsAg/AS37B*	X	X	
HBs-AS37_100	23-30		HBsAg/AS37A**	X	X	

\*AS37B refers to aluminum hydroxide + 50 µg [CCI](#)

\*\*AS37A refers to aluminum hydroxide + 100 µg [CCI](#)

The study will be conducted following a staggered design, and the initiation of the HBs-AS37\_100 group will be conditional to whether any holding rule is met in the HBs-AS37\_50 group.

Study holding rules are defined in [Table 3](#). Holding rules 1a-d will be assessed by the investigator on a continuous basis and meeting any of these holding rules will trigger a hold of vaccination irrespective of number of participants enrolled and/or timing of the event relative to vaccination. Holding rules 2a-d will be assessed by the SRT during the scheduled meetings for evaluation of safety data.

**Table 3** **Study holding rules**

Holding rule	Event	Number/percentage of participants per group
1a	Death or any life-threatening SAE regardless of causality	≥1
1b	Any serious adverse event (SAE) considered at least possibly related to the study intervention as per Investigator or Sponsor assessment	≥1
1c	Any withdrawal from the study (by investigator or participant request) following a Grade 3 AE	≥1
1d	Any administration site or systemic solicited AE leading to hospitalization or necrosis at the injection site, each with an event onset within the 7-day (Day 1-7) post-study intervention period	≥1
2a	Any Grade 3 solicited administration site AE (lasting 48h or more as Grade 3) in an investigational group, with an event onset within the 7-day (Day 1-7) post-study intervention period	20%
2b	Any Grade 3 solicited systemic AE (lasting 48h or more as Grade 3) in an investigational group, with an event onset within the 7-day (Day 1-7) post-intervention period	20%
2c	Any Grade 3 unsolicited AE in an investigational group, that can be reasonably attributed to the study intervention, with an event onset within the 7-day (Day 1-7) post-study intervention period or Any Grade 3 or above abnormality in pre-specified hematological or biochemical laboratory parameters* in an investigational group at Day 8 post-study intervention	20%
2d	Any Grade 3 non-serious AE considered as, at least, possibly related to the study intervention as per Investigator or Sponsor assessment, independent of within or not within the same system-organ-class	≥2

AE = adverse event; SAE = serious adverse event

### 1.2.2. Sequence of analyses

There will be no interim analyses.

A main analysis is planned on data collected post-Dose 2 (Day 61 – Visit 7) and a final analysis including data up to study end (Day 361 - Visit 9). However, there will be interim safety monitoring reviews as described in [Section 1.2.1](#). A separate SAP is developed to describe the analyses for the interim safety monitoring reviews.

### 1.2.2.1. Main analysis

The main analysis will be performed on safety and reactogenicity data (primary endpoints) and immunogenicity data (secondary endpoints) when all data post-Dose 2 (Day 61 – Visit 7) are cleaned and available. CCI [REDACTED]

### 1.2.2.2. Final analysis

The final analysis on primary, secondary and CCI [REDACTED] (safety, reactogenicity and immunogenicity data) will be performed when all data up to Day 361 (Visit 9) are cleaned and available.

An integrated CSR containing all data will be written and made available to the investigators.

## 2. STATISTICAL HYPOTHESES

No confirmatory statistical hypotheses are to be tested. All analyses are descriptive.

### 2.1. Multiplicity Adjustment

In general, results will not be adjusted for multiple comparisons.

## 3. ANALYSIS SETS

Analysis Set	Description	Analyses Evaluated
Screened	All participants who were screened for eligibility.	Study Population
Enrolled	All participants who entered the study (who were randomized or received study intervention or underwent a post-screening procedure). NOTE: Screening failures (who never passed screening even if rescreened) and participants screened but never enrolled into the study (i.e., met eligibility but not needed) are excluded from the Enrolled Set as they did not enter the study.	Study Population
Exposed (ES)	All participants who received at least 1 dose of the study intervention. Analysis per group using the Enrolled Set is based on the administered intervention.	Safety
Per-Protocol (PPS)	All eligible participants who received all doses as per protocol, had immunogenicity results post-dose, complied with dosing/blood draw intervals, without intercurrent conditions that may interfere with immunogenicity and without prohibited concomitant medication/vaccination.	Immunogenicity

CCI [REDACTED]

### **3.1. Criteria for eliminating data from Analysis Sets**

Elimination codes will be used to identify participants to be eliminated from the analyses. Details are provided below for each analysis set. See [Table 4](#) for a list and description of all elimination codes.

#### **3.1.1. Elimination from Enrolled set**

Code 800 (fraudulent data), and code 900 (invalid informed consent) will be used to identify participants eliminated from the Enrolled Set.

#### **3.1.2. Elimination from Exposed Set (ES)**

Code 1030 (study intervention not administered at all, but participant number allocated), code 800 (fraudulent data) and code 900 (invalid informed consent or post-hoc refusal for data use) will be used to identify participants eliminated from the ES.

#### **3.1.3. Elimination from Per-protocol Set (PPS)**

A participant will be excluded from the per-protocol set (PPS) for analysis of humoral immunogenicity in the following manner:

- For codes 800, 900, 1030, 1050 and 2010: participants will be eliminated for all visits.
- For codes 1040, 1070, 1080, 1090, 2040, 2050 and 2080: participants will be eliminated from the specific visit at which the condition is met and onwards.
- For codes 2090, 2100, 2110, 2120: participants will be eliminated at the specific visit at which the condition is met.

CCI

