8.1.1. Biological samples

An overall volume of ~490.5 mL per participant will be collected during the entire study period, over a one-year period. Refer to [Table 6](#) and SoA (Section 1.3) for details of volumes collected for different assessments.

Table 6 Biological samples

Sample type	Quantity	Unit	Timepoint	
Blood sampling for anti-HBs Ab, anti-HBc Ab and-HBs Antigen screening tests	~8.5	mL	SCREEN (Day -7)	All screened
Blood sampling for antibody determination CCI	~20		Day 1, Day 31, Day 61 and Day 361	All participants
Blood sampling CCI	~5			
Blood sampling CCI	~5			
Blood sampling for CMI response	~50		Day 1, Day 8, Day 31, Day 38, Day 61 and Day 361	All participants
Blood sampling for hematology/biochemical analysis at screening and for safety monitoring	~7		SCREEN (Day -7)	All screened
			Day 1, Day 8, Day 31, Day 38, and Day 61	All participants

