**Table 4 List of elimination codes**

Code	Condition under which the code is used	Visit when it is applicable	Applicable for analysis set/endpoint
800	Fraudulent data	All	Enrolled set, ES and PPS, CCI
900	Invalid informed consent	All	Enrolled set, ES and PPS, CCI
1030	Study intervention not administered at all, but participant number allocated	All	ES, PPS, CCI
1040	Administration of concomitant vaccine(s) forbidden in the protocol: 
 
Use of any investigational or non-registered vaccine other than the study interventions during the period beginning 30 days before the first dose of study intervention, or their planned use during the study period.
 
Planned administration/administration of a vaccine* not foreseen by the Protocol in the period starting 30 days* before each dose and ending 30 days* after each dose of study intervention administration**.               
With the exception of influenza vaccine (pandemic or seasonal).
 
**In case an emergency mass vaccination for an unforeseen public health threat (e.g., a pandemic) is recommended and/or organized by public health authorities outside the routine immunization program, the time period described above can be reduced if, necessary for that vaccine, provided it is used according to the local governmental recommendations and that the Sponsor is notified accordingly.
 
 
	From the specific visit the condition is met	ES, PPS, CCI
1050	Randomization failure: Participant not treated according to regimen assigned by randomization	From the specific visit (1, 4 or 8) the condition is met	PPS and CCI
1070	Vaccine administration not according to protocol Incomplete vaccination course Participant was vaccinated with the correct vaccine but containing a lower volume Wrong replacement or study vaccine administered (not compatible with the vaccine regimen associated to the treatment number) Route of the study vaccine is not intramuscular Wrong reconstitution of administered vaccine	From the specific visit (1, 4 or 8) the condition is met and from the specific visit (1 or 4) the condition is met but only up until the visit before the next dose for CCI	PPS, CCI

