1080	Vaccine temperature deviation Vaccine administered despite a Good Manufacturing Practices (GMP) no-go temperature deviation	From the specific visit (1, 4 or 8) the condition is met for PPS and from the specific visit (1 or 4) the condition is met but only up until the visit before the next dose for CCI	PPS, CCI
1090	Expired vaccine administered	From the specific visit (1, 4 or 8) the condition is met for PPS and from the	PPS, CCI

Code	Condition under which the code is used	Visit when it is applicable	Applicable for analysis set/endpoint
		specific visit (1 or 4) the condition is met but only up until the visit before the next dose for CCI	
2010	Protocol violation linked to inclusion/exclusion criteria All inclusion/exclusion criteria defined in the protocol to be checked except for CCI	All	PPS
5010	Protocol violation linked to inclusion/exclusion criteria All inclusion/exclusion criteria defined in the protocol to be checked including for CCI	All	CCI
2040	Administration of any medication forbidden by the protocol 
 
Use of any investigational or non-registered product (drug, vaccine or medical device) other than the study intervention during the period beginning 30 days before the first dose, or use during the study period.
 
Administration or planned administration of long-acting immune-modifying drugs at any time during the study period (e.g., infliximab).
 
Administration of immunoglobulins and/or any blood products or plasma derivatives during the period starting 3 months before the first dose of study intervention or planned administration during the study period.
 
Chronic administration (defined as more than 14 days in total) of immunosuppressants or other immune-modifying drugs during the period starting 3 months prior to the first study intervention dose. For corticosteroids, this will mean prednisone equivalent <math>\geq</math> 20 mg/day, or equivalent. Inhaled, intra-articular and topical steroids are allowed.
 
	From the specific visit the condition is met.	PPS
2050	Intercurrent medical condition: Participants may be eliminated from the PPS for immunogenicity if, during the study, they incur an intercurrent medical condition that could alter their immune response (i.e., varicella, HIV, lymphoma) or are confirmed to have an alteration of their initial immune status.	From the specific visit the condition is met.	PPS

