2080	Participants did not comply with vaccination schedule: 
 
Number of days between Visit 1 and Visit 4 is outside [21-42 days] for all study groups
 
Number of days between Visit 4 and Visit 8 is outside [136-164 days], for HBs-alum group
 
	From the specific visit the condition is met.	PPS
2090	Participants did not comply with blood sample schedule (any of the below options): 
 
Number of days between Visit 1 and Visit 4 is outside [21-42] days
 
Number of days between Visit 4 and Visit 7 is outside [21-42 days]
 
Number of days between Visit 7 and Visit 9 is outside [286-314 days]
 
	At the specific visit (4 or 7 or 9) the condition is met	PPS
2100	Serological antibody results not available.	At the specific visit (1 or 4 or 7 or 9) the condition is met	PPS

Code	Condition under which the code is used	Visit when it is applicable	Applicable for analysis set/endpoint
2110	Blood sample for serological antibodies available but not yet tested (main analysis)	At the specific visit (1, or 4, or 7, or 9) the condition is met	PPS
2120	Issues in the lab results that are not related to handling of lab samples (Eg: Hemolysis, calibration of instruments) Unreliable released data as a result of confirmed sample mismatch or confirmed inappropriate sample handling at lab	At the specific visit the condition is met	PPS

CCI

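### The SAP gives code 1050 two different PPS visit rules, and a Dose 2 fault under codes 1070, 1080 or 1090 removes the Day 31 antibody result drawn before that dose (minor)

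*SAP*

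**What the plan says.** SAP 3.1.3 sets the visits lost from the Per-Protocol Set (PPS) for each elimination code, and Table 4 repeats them code by code.

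- **Codes 1070, 1080 and 1090** (administration not per protocol, temperature deviation, expired vaccine). SAP 3.1.3: "participants will be eliminated from the specific visit at which the condition is met and onwards". Table 4 agrees. The 1070 cell opens "From the specific visit (1, 4 or 8) the condition is met", and the 1080 and 1090 cells read "From the specific visit (1, 4 or 8) the condition is met for PPS". Code 1070 includes "Incomplete vaccination course".
- **Code 1050** (not treated as randomized). SAP 3.1.3: "For codes 800, 900, 1030, 1050 and 2010: participants will be eliminated for all visits". Table 4: "From the specific visit (1, 4 or 8) the condition is met".

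Protocol Table 6 schedules antibody samples at "Day 1, Day 31, Day 61 and Day 361", that is Visits 1, 4, 7 and 9, with none at Visit 8. Protocol Table 9 labels the Visit 4 sample as pre-Dose 2. Day 31 GMC, seroconversion and seroprotection are secondary endpoints, and Protocol 9.3.2 plans pairwise group comparisons after Dose 1.

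**The concern.** The Day 31 sample measures the response to Dose 1. A fault in Dose 2, given later at the same visit, cannot change it, yet the rule starts at Visit 4 and so takes the Day 31 result out.

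Other codes already deal with unusable Day 31 data. Codes 2080 and 2090 both remove results outside the 21 to 42 day window from Visit 1 to Visit 4, and code 2100 covers "Serological antibody results not available". What codes 1070, 1080 and 1090 add at Day 31 is the loss of available, in-window results. Such participants can exist, because Protocol 7.1 lets someone who stops vaccination continue with immunogenicity procedures.

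For code 1050 the issue is reproducibility. Two programmers, one following SAP 3.1.3 and one following Table 4, would build different PPS datasets. Under the 3.1.3 rule, Day 31 and Day 61 results used in the main analysis could also disappear from the final analysis after a Visit 8 event.

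**Working it through.** The plan states no figure for this point, so there is none to reproduce.

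**Which results each rule removes.** Samples are at Visit 1 (Day 1), Visit 4 (Day 31), Visit 7 (Day 61) and Visit 9 (Day 361).

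| Event at | All visits (3.1.3, code 1050) | From that visit (Table 4, code 1050; both places for 1070/1080/1090) | From the first sample after the dose |
|---|---|---|---|
| Visit 1 | Days 1, 31, 61, 361 | Days 1, 31, 61, 361 | Days 31, 61, 361 |
| Visit 4 | Days 1, 31, 61, 361 | Days 31, 61, 361 | Days 61, 361 |
| Visit 8 (HBs-alum) | Days 1, 31, 61, 361 | Day 361 | Day 361 |

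For code 1050 the two SAP rules differ by 0, 1 and 3 timepoints for events at Visits 1, 4 and 8. For a Visit 4 event both remove Day 31, and only Day 1 is in dispute. For codes 1070, 1080 and 1090 at Visit 4, the present rule and the post-dose rule differ by Day 31 alone.

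**Precision of the Day 31 GMC.** Inputs are 23 to 30 participants per group (SAP 5) and a 95% t-interval on log10 data (SAP 4.1.1). With the SD unchanged, the half-width in SD units is t(0.975, n−1)/√n.

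- n = 23: 0.4324. With 22 left, 0.4434 (ratio 1.025). With 21 left, 0.4552 (ratio 1.053).
- n = 30: 0.3734. With 29 left, 0.3804 (ratio 1.019). With 28 left, 0.3878 (ratio 1.038).

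**Pairwise GMC ratio, one group losing one.** Assuming an unadjusted pooled t-interval, [t(0.975, 43)·√(1/22 + 1/23)] / [t(0.975, 44)·√(2/23)] = 1.012. For 29 against 30 the corresponding ratio is 1.009.

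**Rates.** With k of n positive, removing one positive participant shifts the rate by k/n − (k−1)/(n−1) = (n−k)/[n(n−1)]. This is largest at k = 1, where it equals 1/n. Removing a negative participant has the same maximum. The largest shift is 4.3 percentage points for n = 23 and 3.3 for n = 30.

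**GMC shift, illustration only.** If the removed participant lies d log10 units from the mean of the others, the group mean moves by d/n, a factor of 10^(d/n). For an assumed d of 0.5 to 1, this is 1.05 to 1.11 for n = 23 and 1.04 to 1.08 for n = 30. The documents do not support any particular d.

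**Would the Exposed Set analysis show the loss?** Protocol 9.3.2 adds it when at least 5% of those vaccinated are out of the PPS at a timepoint. SAP 1.1 adds it when more than 10% in any group, among those with serology, are excluded. Suppose these are the only exclusions and both triggers are read per group:

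- One lost: 1/23 = 4.3% or 1/30 = 3.3%. Neither trigger is reached.
- Two lost: 2/23 = 8.7% or 2/30 = 6.7%. Only the protocol trigger is reached.
- Three lost: 3/23 = 13.0% reaches both; 3/30 = 10.0% reaches only the protocol trigger.

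If the protocol's 5% is taken over all vaccinated participants instead, 6 of 115 (5.2%) or 8 of 150 (5.3%) are needed.

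**The case against.** **The rule may be a design choice.** The secondary estimand in SAP 1.1, the PPS definition in SAP 3 and Protocol Table 14 all require every dose to have been given per protocol. Read literally, someone with a faulty Dose 2 is outside the population at every visit. It is right that 3.1.3 and Table 4 agree with each other on codes 1070, 1080 and 1090, so this part is not a contradiction between them. But the SAP does not apply the literal definition. It eliminates by visit and keeps Day 1. Given that approach, starting at Visit 4 removes one sample that the fault could not have touched.

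**The Exposed Set analysis is a safeguard.** This stands for larger losses, but it can miss a single loss in a group.

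**The code 1050 conflict will rarely matter.** This is largely fair. Screening excludes anti-HBs-positive people, so Day 1 should carry little information. At Visit 8 only HBs-alum is dosed, and only with Engerix-B, so a wrong-regimen event there is improbable. An omitted third dose fits code 1070. The two texts still cannot both be followed.

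**Changing the PPS now would be post hoc.** The rationale for Protocol Amendment 4 cites main-analysis immunogenicity results, so Day 61 results of an open-label study are known. This stands, and it favours a supplementary analysis over a new PPS rule.

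A reader might also infer that the rule biases the adjuvant comparison at Day 31. Loss through an incomplete course could be related to adjuvant if reactogenicity leads to Dose 2 being withheld, but the documents do not show that it was. For codes 1080 and 1090 nothing links the event to the Day 31 response, and the visible cost is precision.

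**Conclusion.** Both parts hold, as a minor point.

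- **Code 1050:** SAP 3.1.3 and Table 4 contradict each other. The datasets differ for a Visit 4 event (Day 1 only) and for a Visit 8 event in HBs-alum (Days 1, 31 and 61).
- **Codes 1070, 1080 and 1090 at Visit 4:** the rule discards an otherwise valid Day 31 result drawn before the dose in question.

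The reading of the text is certain; the practical size is not. The number of participants affected is not in the documents and may be zero. The precision figures assume one or two losses and an unchanged SD. The trigger comparison assumes no other PPS exclusions. The GMC factors rest on an assumed distance and should carry no weight in the decision. The documents do not support a claim of biased group comparisons, nor a claim that the PPS must be redefined.

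**What to change.** 1. Give code 1050 one identical visit rule in SAP 3.1.3 and Table 4. If anyone carries the code, state which rule the main-analysis dataset used.
2. For codes 1070, 1080 and 1090, add a Day 31 analysis in which elimination starts at the first serology sample after the affected dose: a Visit 1 dose from Visit 4, a Visit 4 dose from Visit 7, a Visit 8 dose at Visit 9. Show it beside the prespecified PPS result, with exclusions by group and code.
3. Label this analysis as added after the main-analysis results were known, and describe it in the clinical study report. If no participant is affected, a sentence saying so replaces the table.

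If the sponsor prefers to change the PPS rule itself, more text must move. The all-doses wording in SAP 1.1 (secondary estimand), SAP 3 and Protocol Table 14 needs aligning. The new rule must be reconciled with the first sentence of Protocol 9.2.1, which allows elimination of participants meeting Section 7.1.1 criteria. SAP 4.8, now marked not applicable, must record the change.

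The recommended route costs a small wording edit, some elimination programming and one extra Day 31 table, with no new data. Its drawback is an addition made after results were known, which the label and the side-by-side display make visible.

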**Table 4 List of elimination codes**

Code	Condition under which the code is used	Visit when it is applicable	Applicable for analysis set/endpoint
800	Fraudulent data	All	Enrolled set, ES and PPS, CCI
900	Invalid informed consent	All	Enrolled set, ES and PPS, CCI
1030	Study intervention not administered at all, but participant number allocated	All	ES, PPS, CCI
1040	Administration of concomitant vaccine(s) forbidden in the protocol: 
 
Use of any investigational or non-registered vaccine other than the study interventions during the period beginning 30 days before the first dose of study intervention, or their planned use during the study period.
 
Planned administration/administration of a vaccine* not foreseen by the Protocol in the period starting 30 days* before each dose and ending 30 days* after each dose of study intervention administration**.               
With the exception of influenza vaccine (pandemic or seasonal).
 
**In case an emergency mass vaccination for an unforeseen public health threat (e.g., a pandemic) is recommended and/or organized by public health authorities outside the routine immunization program, the time period described above can be reduced if, necessary for that vaccine, provided it is used according to the local governmental recommendations and that the Sponsor is notified accordingly.
 
 
	From the specific visit the condition is met	ES, PPS, CCI
1050	Randomization failure: Participant not treated according to regimen assigned by randomization	From the specific visit (1, 4 or 8) the condition is met	PPS and CCI
1070	Vaccine administration not according to protocol Incomplete vaccination course Participant was vaccinated with the correct vaccine but containing a lower volume Wrong replacement or study vaccine administered (not compatible with the vaccine regimen associated to the treatment number) Route of the study vaccine is not intramuscular Wrong reconstitution of administered vaccine	From the specific visit (1, 4 or 8) the condition is met and from the specific visit (1 or 4) the condition is met but only up until the visit before the next dose for CCI	PPS, CCI
1080	Vaccine temperature deviation Vaccine administered despite a Good Manufacturing Practices (GMP) no-go temperature deviation	From the specific visit (1, 4 or 8) the condition is met for PPS and from the specific visit (1 or 4) the condition is met but only up until the visit before the next dose for CCI	PPS, CCI
1090	Expired vaccine administered	From the specific visit (1, 4 or 8) the condition is met for PPS and from the	PPS, CCI

Code	Condition under which the code is used	Visit when it is applicable	Applicable for analysis set/endpoint
		specific visit (1 or 4) the condition is met but only up until the visit before the next dose for CCI	
2010	Protocol violation linked to inclusion/exclusion criteria All inclusion/exclusion criteria defined in the protocol to be checked except for CCI	All	PPS
5010	Protocol violation linked to inclusion/exclusion criteria All inclusion/exclusion criteria defined in the protocol to be checked including for CCI	All	CCI
2040	Administration of any medication forbidden by the protocol 
 
Use of any investigational or non-registered product (drug, vaccine or medical device) other than the study intervention during the period beginning 30 days before the first dose, or use during the study period.
 
Administration or planned administration of long-acting immune-modifying drugs at any time during the study period (e.g., infliximab).
 
Administration of immunoglobulins and/or any blood products or plasma derivatives during the period starting 3 months before the first dose of study intervention or planned administration during the study period.
 
Chronic administration (defined as more than 14 days in total) of immunosuppressants or other immune-modifying drugs during the period starting 3 months prior to the first study intervention dose. For corticosteroids, this will mean prednisone equivalent <math>\geq</math> 20 mg/day, or equivalent. Inhaled, intra-articular and topical steroids are allowed.
 
	From the specific visit the condition is met.	PPS
2050	Intercurrent medical condition: Participants may be eliminated from the PPS for immunogenicity if, during the study, they incur an intercurrent medical condition that could alter their immune response (i.e., varicella, HIV, lymphoma) or are confirmed to have an alteration of their initial immune status.	From the specific visit the condition is met.	PPS
2080	Participants did not comply with vaccination schedule: 
 
Number of days between Visit 1 and Visit 4 is outside [21-42 days] for all study groups
 
Number of days between Visit 4 and Visit 8 is outside [136-164 days], for HBs-alum group
 
	From the specific visit the condition is met.	PPS
2090	Participants did not comply with blood sample schedule (any of the below options): 
 
Number of days between Visit 1 and Visit 4 is outside [21-42] days
 
Number of days between Visit 4 and Visit 7 is outside [21-42 days]
 
Number of days between Visit 7 and Visit 9 is outside [286-314 days]
 
	At the specific visit (4 or 7 or 9) the condition is met	PPS
2100	Serological antibody results not available.	At the specific visit (1 or 4 or 7 or 9) the condition is met	PPS

Code	Condition under which the code is used	Visit when it is applicable	Applicable for analysis set/endpoint
2110	Blood sample for serological antibodies available but not yet tested (main analysis)	At the specific visit (1, or 4, or 7, or 9) the condition is met	PPS
2120	Issues in the lab results that are not related to handling of lab samples (Eg: Hemolysis, calibration of instruments) Unreliable released data as a result of confirmed sample mismatch or confirmed inappropriate sample handling at lab	At the specific visit the condition is met	PPS

CCI

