**CCI**

### ***Primary estimand***

The primary clinical question of interest is to assess the reactogenicity and safety in all study groups among participants who received at least one dose of the study interventions (i.e., the Exposed Set [ES]).

The estimand is described by the following attributes:

- Population: ES.
- Treatment condition: 5 study interventions as described in [Table 1](#).

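### SAP Table 4 removes participants given a forbidden vaccine (code 1040) from the Exposed Set, against SAP 3.1.2 and the set's own definition; probably a slip in one cell

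*SAP*

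**What the plan says.** SAP Table 4 defines code 1040 as "Administration of concomitant vaccine(s) forbidden in the protocol". Its visit column reads "From the specific visit the condition is met", and its last column names the ES and the PPS, plus a redacted entry. The ES entry is legible, so the redaction does not affect this point.

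SAP 3.1.2 lists the codes that remove a participant from the ES: "Code 1030 (study intervention not administered at all, but participant number allocated), code 800 (fraudulent data) and code 900". Code 1040 is not among them.

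SAP 3 defines the ES as "All participants who received at least 1 dose of the study intervention", and Protocol Table 14 uses the same words. The primary estimand in SAP 1.1 is set in "participants who received at least one dose of the study interventions". SAP 3.1.3 handles 1040 as a PPS code: "For codes 1040, 1070, 1080, 1090, 2040, 2050 and 2080: participants will be eliminated from the specific visit".

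On how text and table relate, SAP 3.1 says "Details are provided below for each analysis set" and sends the reader to Table 4 "for a list and description of all elimination codes". It gives no order of precedence.

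**The concern.** The ES carries the primary objective (Protocol 9.3.1, SAP 4.2.1). A rule that takes dosed participants out of it because of a later or concurrent vaccine changes who is counted in the primary safety percentages. A programmer working from Table 4 and one working from SAP 3.1.2 would build different safety populations.

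The ES is also the population for the additional immunogenicity analysis, if its PPS-exclusion trigger is met (SAP 1.1, secondary estimand; Protocol 9.3.2). That analysis is meant to complement the PPS by bringing excluded participants back. Following the cell would carry one of the PPS exclusions into it.

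The rule could also fall unevenly. Part of code 1040 covers the 30 days before and after each dose, and only HBs-alum has a dose at Visit 8, so that group has an extra window in which the code can apply.

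**Working it through.** **1. Text comparison.** The plan states no figure to reproduce, so the check is mainly of wording.

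| Source | Treatment of a forbidden concomitant vaccine |
|---|---|
| SAP Table 4, code 1040 | Eliminates from ES and PPS, from the visit concerned |
| SAP 3.1.2 | ES loses codes 1030, 800 and 900 only |
| SAP 3 and Protocol Table 14, ES definition | At least one dose; no condition on other vaccines |
| SAP 3 and Protocol Table 14, PPS definition | Freedom from prohibited vaccination is required here only |
| SAP 3.1.3 | Code 1040 used for the PPS |
| Protocol 9.2.1 | Speaks of elimination from the Per-Protocol analysis only |
| SAP 4.2.1, unsolicited AEs | Denominator is all exposed participants |
| SAP 4.8 | Declares no changes to protocol-defined analyses |

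One cell stands against all the rest. Its visit-wise timing also fits poorly with a set that a participant enters by receiving one dose, and the SAP has no rule for removing someone from the ES at a given visit.

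**2. Size.** The inputs are the planned minimum and maximum per group, n = 23 and n = 30 (SAP 5). The documents do not give the number of code 1040 cases. One case in a group is assumed throughout.

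The intervals are exact (Clopper-Pearson) 95%. For zero events the upper limit is 1 − 0.025^(1/n). For example, 1 − 0.025^(1/23) = 14.8% and 1 − 0.025^(1/22) = 15.4%. For one event the limits are the 2.5% quantile of Beta(1, n) and the 97.5% quantile of Beta(2, n − 1).

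| Assumed scenario | n = 23 | n = 30 |
|---|---|---|
| (a) Full removal, no events in the group | 0/23 (upper limit 14.8%) becomes 0/22 (15.4%) | 0/30 (11.6%) becomes 0/29 (11.9%) |
| (b) Full removal, only event is in another participant | 1/23 = 4.3% (0.1% to 21.9%) becomes 1/22 = 4.5% (0.1% to 22.8%) | 1/30 = 3.3% (0.1% to 17.2%) becomes 1/29 = 3.4% (0.1% to 17.8%) |
| (c) Condition met at Visit 1, removed participant has the only event | 1/23 becomes 0/22 (0% to 15.4%) | 1/30 becomes 0/29 (0% to 11.9%) |
| (d) Later removal drops the event but keeps the participant in the denominator | 1/23 becomes 0/23 (0% to 14.8%) | 1/30 becomes 0/30 (0% to 11.6%) |

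In (a) and (b) every upper limit moves by less than one percentage point. In (c) and (d) an observed event disappears from the percentage. Because there is no visit-wise rule for the ES, the documents cannot show whether (c) or (d) would apply.

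**The case against.** The best counter-argument is that the documents already settle the matter. SAP 3.1.2 is a closed list, only the PPS definition mentions prohibited vaccination, Protocol 9.2.1 confines elimination to the Per-Protocol analysis, and SAP 4.8 declares no departure from the protocol. The cell can hardly be carried out for the ES anyway. No cases are known, and scenarios (c) and (d) need several things to be true together: a case exists, the cell was programmed, and the same person had the group's only event.

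Most of this stands, and it is why the cell is read as a slip and the point as minor. It does not remove the contradiction. The cell is a stated analysis-set rule that is wrong as written, in the table to which SAP 3.1 sends the reader for the codes.

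A further argument is that nothing would be lost from view, since SAP 4.2.1 provides listings of SAEs, MAEs, pIMDs and concurrent vaccines, and SAP 6.1.1 reports the size of each analysis set. The set sizes would help a reader notice a removal. The listings are weaker reassurance: they sit in a section whose analyses are performed on the ES, no separate population is named for them, and the event listing does not cover solicited events or non-serious unsolicited events that were not medically attended.

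**Conclusion.** The concern holds and is minor. Table 4 contradicts SAP 3.1.2 and the ES definition on code 1040, and the evidence within the documents points clearly to the table cell as the error. Confidence is high for the mismatch, but not for any effect on results. The number of cases is not given, the rule actually programmed is not shown, and the effect may be zero. With one assumed case per group the loss of precision is negligible. The only consequential outcome is the loss of a single event from a tabulated percentage, such as 1/23 shown as 0/22, and that rests on the stacked assumptions in (c) or (d).

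**What to change.** Delete ES from the code 1040 row of SAP Table 4 and leave the redacted entry as it is. Confirm which rule was programmed for the ES outputs, including any ES immunogenicity analysis. Re-run them only if the table rule was used and at least one code 1040 case occurred.

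Protocol Amendment 4 (17 Sep 2024) already refers to main analysis results, and the last SAP version listed is dated 28 Jun 2024. The correction should therefore be recorded in a dated SAP amendment or explained in the clinical study report, as Protocol 9.3 requires for changes to the statistical plan.

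While the table is open, check its other rows against SAP 3.1.1 to 3.1.3. Code 1050, for example, eliminates for all visits in 3.1.3 but from a specific visit in Table 4.

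The cost is one table cell, one program check and a short record. No new data are needed.
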